## 2. Specific Aims and Objectives

**1. To test the effect of a single t-PBM session on cerebral blood flow (CBF), while irradiating R-dlPFC, in subjects with impulsivity due to BD**

*Hypothesis:* a single t-PBM session on the R-dlPFC will significantly increase BOLD-signal at the R-dlPFC, relative to sham.

**2. To test the effect of repeated t-PBM sessions on CBF, after irradiating R-dlPFC, in subjects with impulsivity due to BD**

*Hypothesis:* repeated t-PBM sessions on the R-dlPFC will significantly increase BOLD-signal at the R-dlPFC at day 5 relative to baseline.

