### *Baseline Visit*

Adverse events, as well as concomitant medications and therapies, will be collected. Participants will complete the Young Mania Rating Scale (YMRS), the BIS, the BRIEF-A, the I-7, the CAST-IRR, and the SAFTEE. A licensed clinician will administer the C-SSRS and the CGI-S. Skin color will be recorded using the NIS-SCS. Participants will complete two computerized gambling tasks: The Iowa gambling task and the Delgado gambling task. The order of administration of the gambling tasks will be randomized. This appointment will last approximately 90 minutes.

*Treatment 1*

Vitals will be assessed and recorded. The MRI Safety Checklist will be completed and signed before the MRI. Participants will undergo an MRI Scan. While in the scanner, participants will first undergo a structural scan and resting state scan, followed by a functional scan during which the participants will receive a sham t-PBM treatment. This scan will be followed by a pre-stimulation resting-state functional acquisition. At this time, active t-PBM will be administered, immediately followed by a post-stimulation resting state scan. Participants will then complete the Delgado gambling task. A functional sequence will be collected during the administration of the gambling task. Finally, participants will undergo a post-stimulation resting state functional scan. The MRI will last approximately 75 minutes in total.

Participants will know that they are receiving both active and sham treatment, but they will not be told in which order the treatments will be delivered. Participants will complete the PBQ, CAST-IRR, TSRQ, and the Iowa Gambling Task at the conclusion of the visit. Study staff will complete an intervention tracking form.

*Treatments 2-4*

Treatments 2, 3, and 4 should ideally occur once daily during the three days following the first treatment administration. If necessary, this window can be extended so that these three treatment visits occur within ten days of the Baseline/Treatment 1 visit (in this case, the timing of follow up visits will be adjusted accordingly). Adverse events and concomitant medications and therapies will be assessed and recorded at each visit. Participants will complete the TSRQ and CAST-IRR after treatment administration. Study staff will complete an intervention tracking form for each study visit.

*Treatment 5*

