*Power and Detectable Effects:* The study is powered (G\*Power 80%) to answer Aim #1 for a moderate effect size (Cohen's  $d \geq 0.5$ ), based on a Wilcoxon signed-rank test (matched pairs; one-tailed; alpha=0.05). Dmochowski et al. demonstrated a BOLD increase as high as 31% (dlPFC) within a single t-PBM session and in healthy subjects (pre- and post-t-PBM; Cohen's  $d=0.374$ ). In our current design, we will compare NIR versus sham (also within a t-PBM session) in 20 subjects with impulsivity due to BD, therefore we anticipate a larger effect size.

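### The expectation that Aim 1's NIR-versus-sham effect will exceed the cited pre-post d of 0.374 is unsupported, and power at the cited value is about 47%, not 80%

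*Combined protocol and SAP*

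**What the plan says.** Aim 1 (Section 2) hypothesises that a single session "will significantly increase BOLD-signal at the R-dlPFC, relative to sham". Section 3 describes the effect on cerebral blood flow as the primary aim, and Aim 1 is the only aim with a power statement.

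That statement is in Section 9, under Power and Detectable Effects. The study is said to be powered at "80%) to answer Aim #1 for a moderate effect size", given as Cohen's d of at least 0.5, using a "Wilcoxon signed-rank test (matched pairs; one-tailed; alpha=0.05"). The support offered is one prior study, which "demonstrated a BOLD increase as high as 31% (dlPFC) within a single t-PBM session and in healthy subjects"; the effect is described as a pre- and post-t-PBM comparison with d = 0.374. The paragraph then turns to the present design, which contrasts NIR with sham inside one session, and draws its conclusion from that contrast and from the population: "in 20 subjects with impulsivity due to BD, therefore we anticipate a larger effect size".

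No section gives an expected sham response, an SD for the NIR-minus-sham difference, a correlation between the two responses, or a pilot effect size. Section 1 mentions other BOLD work and an ongoing sham-controlled study in depression, but reports no effect size from either.

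**The concern.** The planning value is larger than the only evidence cited for it, and one sentence carries the step from 0.374 to 0.5. That sentence offers two reasons, the sham contrast and the bipolar population, and argues neither.

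The sham contrast is not an obvious gain. A pre-post change within one session is already a within-subject comparison, so pairing adds nothing new. The pre-post mean also contains any non-specific change, such as drift, warming or time in the scanner, which a sham contrast is meant to remove. The difference between two responses also carries the variability of both.

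What is at stake is how an Aim 1 result is read. As the paragraph stands, a reader will take 80% power as backed by the citation. If the true effect is near the cited one, a non-significant result is about as likely as a significant one and says little about target engagement.

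**Working it through.** **Inputs.** From Section 9: planning d = 0.5, cited d = 0.374, one-sided signed-rank test, alpha 0.05, stated power 80%, 20 subjects. Assumed, because the documents do not say: 0.374 is mean change divided by the SD of the change; NIR and sham responses have equal SD; the shape of the paired differences is as labelled below.

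**The plan's own figure first.** Two methods were used: the asymptotic-relative-efficiency (ARE) approach (noncentral t with n' = n × ARE, df = n' − 1, noncentrality d√n'), and simulation with the exact critical value (W ≥ 150, actual size 0.0487). At d = 0.5 and n = 20:

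| Distribution of differences | ARE method | Exact simulation | Pairs for 80% (ARE) |
|---|---|---|---|
| Normal | 68% | 67% | 28 |
| Logistic | 73% | 72% | 24 |
| Laplace | 85% | 78% | 18 |

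The 80% is not reproduced under a normal or logistic distribution. Only the Laplace case, which the plan does not state, brings the required number near 20. This is a separate matter, and nothing below depends on it.

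**Power at the cited effect.** At d = 0.374, n = 20, exact simulation gives about 47% (normal), 51% (logistic) and 58–59% (Laplace). With normal differences, 80% power at d = 0.374 needs about 48 pairs.

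**From a pre-post d to a NIR-minus-sham d.** Let each response have SD σ, let ρ be the within-person correlation between them, and let the mean sham response be a fraction f of the mean NIR response. The difference has variance 2σ²(1 − ρ), so

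d(NIR − sham) = 0.374 × (1 − f) / √(2(1 − ρ)).

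With no sham response (f = 0), 20 pairs and normal differences:

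| ρ | d(NIR − sham) | Power |
|---|---|---|
| 0 | 0.374/√2 = 0.264 | about 30% |
| 0.25 | 0.374/√1.5 = 0.305 | about 36% |
| 0.5 | 0.374/√1 = 0.374 | about 47% |
| 0.75 | 0.374/√0.5 = 0.529 | about 72% |

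Setting d = 0.5 and solving: ρ = 1 − (0.374/0.5)²/2 = 0.72. If the sham response is a quarter of the NIR response, the required ρ is 1 − (0.374 × 0.75/0.5)²/2 = 0.84; at one half it is 0.93.

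**Can the scan sequence fix ρ?** Not without a stated baseline. In Treatment 1 (Section 6) there is a resting scan before sham, and after the sham scan "This scan will be followed by a pre-stimulation resting-state functional acquisition"; a further rest scan follows NIR. Call the three rest scans R0, R1 and R2, with independent noise of equal variance, and consider the after-stimulation changes.
- Each change from its own preceding rest scan: R1 − R0 and R2 − R1. R1 enters with opposite signs, ρ = −0.5, d = 0.374/√3 = 0.216, power about 23%.
- Both changes from the common pre-sham scan: R1 − R0 and R2 − R0. R0 is shared, ρ = +0.5, d = 0.374, power about 47%.

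Section 9 does not say which baseline applies, and its outcome also includes signal during stimulation, which neither case covers.

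**The case against.** A reader might go further and infer that the plan's reasoning is backwards, so that a sham contrast must give a smaller effect. The documents do not support that. Removing non-specific change lowers the mean only if the sham response is positive; if BOLD falls under sham, the contrast grows. The standardised effect also exceeds 0.374 whenever ρ is above 0.5 with little sham response, and such a correlation between two responses in the same person and session cannot be ruled out. The bipolar-population half of the argument is unsupported, but nothing shows that it points the other way.

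The numbers can be challenged too. Section 9 does not name the standardiser of 0.374. If it is the raw-score SD, the paired effect for that same pre-post change is 0.374/√(2(1 − r)), with r the pre-post correlation: 0.26 at r = 0, 0.48 at r = 0.7, 0.59 at r = 0.8. So 47% could be too low or too high. Quoting only the ρ = −0.5 case would be one-sided, since a common baseline gives +0.5 on the same noise assumption.

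Finally, choosing d = 0.5 as a target is legitimate; the paragraph's heading already speaks of detectable effects, and no section says that a null Aim 1 result would be taken as absence of target engagement.

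All of this stands, and it limits the direction and the size of the point. It does not supply what is missing: a reason in the documents to expect more than 0.374.

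**Conclusion.** The expectation of a larger effect is unsupported. The NIR-minus-sham effect could be below or above 0.374, and nothing in the documents supports 0.5. Getting there from 0.374 by way of the sham contrast needs a correlation of about 0.72 with no sham response, and more with one.

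The power figures rest on 20 complete pairs and on 0.374 being standardised by the SD of the change; the figures below 0.374 also assume equal variances and no sham response. On the evidence cited, the chance of detecting the effect is roughly even rather than four in five.

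This should be fixed. It changes what the power statement can claim and what a null result can show, but not the design, test or estimand.

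**What to change.** In Section 9, Power and Detectable Effects:

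- Delete the closing clause that predicts a larger effect.
- State that d = 0.5 is a detectable-effect target and not an expectation drawn from the cited study.
- Report power at d = 0.374 and over a stated, balanced range of correlations, for example ρ = 0 to 0.75. Name the standardiser of the cited d and the distribution assumed for the paired differences.
- If the ρ = −0.5 case is shown, label it as conditional on each change using its own preceding rest scan, and put the common-baseline case (ρ = +0.5) beside it.
- Commit to reporting the NIR-minus-sham estimate with its confidence interval, and state that a non-significant Aim 1 result does not rule out an effect of the cited size.

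The cost is one rewritten paragraph and a less favourable power statement. No extra subjects, scans or visits are needed.

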## **10. Monitoring and Quality Assurance**

At enrollment, each subject will be assigned a unique ID number that will be used in place of a subject's name across all study forms and documents. Documents will be stored separately from other materials in a locked filing cabinet that is only accessible by study staff. Subjects may request that their data be withdrawn by contacting [name] (contact information provided on the consent form). Experienced, doctoral-level clinicians will be available to participants by phone, or in-person if necessary, to discuss any concerns throughout the study. This will be clearly communicated orally and in writing to subjects.

The data gathered from the project will include imaging and treatment data. Information relating to the data derived from this study will be made available to Partners IRB. The information collected in the study will be used only for research purposes. There are no plans to share any of the collected data with anyone outside of the immediate study staff.

[name], PhD (Neuropsychiatry), Director of Photobiomodulation at MGH Depression Program and at MGH Neuropsychiatry will provide his expertise on t-PBM and its effects on psychiatric conditions. [name], MPH is Chief of the Division of Neuropsychiatry at MGH and directs the Laboratory of Neuropsychiatry and Neuromodulation. His will provide his expertise in imaging studies of neuromodulation. [name] Is the director of Dimensional Neuroimaging Research within the Division of Neuropsychiatry and will provide her expertise in bipolar disorder and neuroimaging. [name], [name], and [name] all have extensive clinical research and data safety monitoring experience. [name], as the principal investigator, will discuss safety concerns with research study team (CRCs and post-doc) and bring any concerns to the other co-Is, if needed. [name] will provide safety monitoring and insight for neuroimaging and [name] will provide her insight for safety of bipolar disorder subjects. In addition to these internal monitors, [name], MSc., will serve as the independent monitor for the study. He is the Director of Clinical Research at the Nathan Kline Institute in New York and has extensive experience within the field of Psychiatry and t-PBM as a PI and co-I of many studies within the field. He will review the annual reports for safety, and findings, and he will provide feedback on the study.

Study staff will meet on a weekly basis for the duration of the study to review the progress of the study, discuss safety concerns that arise, and make recommendations to improve safety procedures if indicated. Study staff will also review and monitor data on a weekly basis to ensure adherence to protocol and accurate data collection.

Subjects will be thoroughly screened prior to starting any study procedures to ensure they meet inclusion criteria and that they have the capacity for voluntary, informed consent.

If the subject experiences any adverse event or discomfort throughout the t-PBM sessions that are not able to be alleviated by the PI or study staff, then the application session will be stopped.

An adverse event means any untoward or unfavorable medical occurrence in a human subject, including any abnormal sign (for example, abnormal physical exam or laboratory finding), symptom, or disease, temporally associated with the subject's participation in the research, whether or not considered related to the subject's participation in the research (modified from the definition of adverse events in the 1996 International Conference on Harmonization E-6 Guidelines for Good Clinical Practice).

A serious adverse event means any event temporally associated with the subject's participation in research that meets any of the following criteria:

- results in death.
- is life threatening (places the subject at immediate risk of death from the event as it occurred).
- requires inpatient hospitalization or prolongation of existing hospitalization.
- results in a persistent or significant disability/incapacity.
- results in a congenital anomaly/birth defect; or
- any other adverse event that, based upon appropriate medical judgment, may jeopardize the subject's health and may require medical or surgical intervention to prevent one of the outcomes listed above (examples of such events include allergic bronchospasm requiring intensive treatment in the emergency room or at home, blood dyscrasias or convulsions that do not result in inpatient hospitalization, or the development of drug dependency or drug abuse).

Expected adverse events and expected serious adverse events will not be accepted by the Mass General IRB nor will they be reported unless the sponsor or investigator deems the event to be unexpected in nature. Only Unanticipated Problem Involving Risks to Subjects or Others (UPIRTSO) and Unanticipated Adverse Device Effect (UADE) Events meeting either of these definitions are considered "Unanticipated Problems" and should be reported if they occur during the conduct of the study, after study completion, or after subject withdrawal or completion. Events meeting these definitions include unexpected or unanticipated drug or device adverse reactions attributable to the intervention and that place subjects at increased risk of harm.

In the case of an unexpected adverse event and in accordance with Partners Human Research Committee Adverse Event Reporting guidelines, the PI and study staff will complete the appropriate adverse event form and send it to the IRB within the required time frame for reporting. This documentation will be completed and submitted on Insight within 5 business/7

calendar days from the day the investigator first became aware of the event. This report will include:

- a detailed description of the event
- the basis for determining that the event is unexpected in nature, severity, or frequency
- the basis for determining that the event is related or possibly related to the research procedures
- the basis for determining that the research places subjects at an increased risk of harm)
- whether any changes to the research or other corrective actions are warranted.

Experienced, doctoral-level clinicians will be available to participants by phone, or in-person if necessary, to discuss any concerns throughout the study. This will be clearly communicated orally and in writing to subjects.

All monitoring and quality assurance procedures will be in accordance with the MGH sub-committee on human studies. The PI will oversee the collection, maintenance, and analysis of the data. Research affairs will be contacted immediately in the case of unexpected adverse events likely related to the intervention. If an unexpected adverse event or serious adverse event does occur, the investigator will consider whether corrective actions should be made to study procedures in order to protect the safety and welfare of study subjects. If any changes are made the Protocol and Informed Consent Form will be updated and these edits will be submitted as an Amendment to the IRB.

If a subject's clinical condition deteriorates substantially by self-report and clinician assessment, the subject will be withdrawn from the study. Subjects may also be withdrawn if the PI feels that the study poses a substantial risk to the participant or if the PI decides that a higher level of care is needed.

Procedures used in this study are consistent with safe and ethical research practices and do not unnecessarily expose subjects to risk. Adverse events are expected to be infrequent given the excellent safety profile of t-PBM, but should they arise, the PI will review the adverse event and report it to the IRB. Moreover, study staff and subjects may report concerns directly to the IRB.

Every effort will be made to enhance the comfort of subjects while throughout the study procedures. Subjects will be informed that they can stop any study procedure at any time if needed.

## **11. Privacy and Confidentiality**

- Study procedures will be conducted in a private setting
- Only data and/or specimens necessary for the conduct of the study will be collected
- Data collected (paper and/or electronic) will be maintained in a secure location with appropriate protections such as password protection, encryption, physical security measures (locked files/areas)

- Specimens collected will be maintained in a secure location with appropriate protections (e.g. locked storage spaces, laboratory areas)
- Data and specimens will only be shared with individuals who are members of the IRB-approved research team or approved for sharing as described in this IRB protocol
- Data and/or specimens requiring transportation from one location or electronic space to another will be transported only in a secure manner (e.g. encrypted files, password protection, using chain-of-custody procedures, etc.)
- All electronic communication with participants will comply with Mass General Brigham secure communication policies
- Identifiers will be coded or removed as soon as feasible and access to files linking identifiers with coded data or specimens will be limited to the minimal necessary members of the research team required to conduct the research
- All staff are trained on and will follow the Mass General Brigham policies and procedures for maintaining appropriate confidentiality of research data and specimens
- The PI will ensure that all staff implement and follow any Research Information Service Office (RISO) requirements for this research
- Additional privacy and/or confidentiality protections

